#### 4.9.2 Deaths

As detailed in the preceding section, a detailed table will be created showing the number of subjects who experienced one SAE leading to Death, the corresponding percentage of subjects and the number of events grouped by SOC and PT.

All deaths will be listed in a summary table.

#### 4.9.3 Local skin reactions as collected in the diary

Number and percentage of subjects with evaluable diary data will be presented.

Local skin reactions at sites of Viaskin® application as assessed by the patient and documented in the diary during the first 6 months of the study treatment will be summarized for itching, redness, swelling, and any local reaction (itching, redness and swelling) using:

- The number and percentage of subjects by maximum severity grade reported (1, 2 or 3) among subjects with evaluable diary data and among subjects with a reaction (grade  $\geq 1$ )
- The number and proportion of days with a reaction reported (based on days with patches graded by type of reaction or for at least one reaction between itching, redness and swelling when reported on any local reaction) among subjects diary data,
- The proportion of days scored by severity grade (worst severity grade per day is considered).

All proportions will be calculated as

$$\left( \frac{\text{Number of days with a reaction reported}}{\text{Number of days with patches graded}} \right)$$

Proportion of days with no assessment of local skin reaction out the number of patches entered in the diary will be provided.

The number of days with a reaction reported and number of days with patches graded will be calculated based on removal dates.

The periods considered for the reporting will be:

- r The overall first 6 months (D1 to D180),
- r Month 1 (D1 to D30),
- r Month 2 (D31 to D60),
- r Month 3 (D61 to D90),
- r Month 4 (D91 to D120),
- r Month 5 (D121 to D150),
- r Month 6 (D151 to D180)

The above analysis will be repeated for subjects with filaggrin gene mutations versus wild type subjects.

All local skin reactions reported by the subject will be listed.

#### 4.9.4 Local skin reactions as graded by the investigator at each visit

Local skin reactions at sites of Viaskin® application are graded by the investigator at each visit. More specifically at Visit 4, this evaluation is performed prior to the application and 30 minutes, 1 hour, 2 hours and 3 hours after the administration. These graded reactions will be reported in summary tables showing the number and percentage of subjects:

- By grade (by localization and regardless of the localization) by study visit
- By most severe grade (by localization and regardless of the localization) for the overall treatment period.

The above analysis will be repeated for subjects with filaggrin gene mutations versus wild type subjects.

All local skin reactions as graded by the investigator will also be listed.

#### 4.9.5 Adverse event of special interest (AESI)

Treatment emergent adverse events of special interest (AESI), as defined in the protocol, are:

- Treatment emergent grade 4 local cutaneous reactions or any significant skin lesion which could potentially lead to skin barrier disruption at sites of patch application (identified with AETERM which contains “GRADE 4” (or “GRADE IV”) and High Level Term equal to “Application and instillation site reactions”),
- Any occurrence of IgE-mediated systemic-type of symptoms distant from the patch application site and considered at least possibly related to the study drug. These systemic allergic TEAEs of interest will be identified through the algorithm of the Anaphylactic Reaction Standardized MedDRA queries (SMQ) (methodology described in the [Appendix 5](#)).

All AESI data will be listed.

An overall overview table of systemic allergic TEAEs cases will also be provided showing the number of subjects, the percentage of subjects and the number of cases for the following categories of systemic AESI, using the definition of the protocol (related only) and in addition showing any systemic allergic reaction considered as unrelated to IP:

- Any systemic allergic TEAE cases considered related to IP
  - ⌞ Reported as Related,
  - ⌞ Reported as Probably related,
  - ⌞ Reported as Possibly related,
- Any systemic allergic TEAE cases considered unrelated to IP:
  - ⌞ Reported as Unlikely related,
  - ⌞ Reported as Unrelated

All systemic allergic TEAEs cases will be listed.

They will be reported in summary tables showing the number and percentage of subjects affected and the number of underlying AE events by SOC and PT, overall and for subjects with filaggrin gene mutations versus wild type subjects. Summary tables will be split for systemic allergic TEAE cases considered related, systemic allergic TEAE cases considered unrelated and treatment emergent local cutaneous reactions.

AESI will be ordered by decreasing frequency on the total population by SOC and by PT within the SOC.

#### 4.9.6 Clinical Laboratory Evaluation

The following laboratory evaluations will be performed at V1 (D-42), V7 (M3), V8 (M6), V10 (M12), Early termination visit, unscheduled visit (in case of AEs, etc.):

- Hematology: hemoglobin, hematocrit, platelets, red blood cells, white blood cells (neutrophils, lymphocytes, monocytes, eosinophils, basophils in value and %);
- Biochemistry: alanine aminotransferase, aspartate aminotransferase, total bilirubin, total protein, blood urea nitrogen, creatinine;

A urine pregnancy test is performed for female subjects of childbearing potential at site at Baseline and M12.

Clinically significant changes (abnormalities) in laboratory parameters, in the judgment of the Investigator, will be recorded as AEs and appropriate countermeasures taken.

In the event of unexplained abnormal laboratory test values of clinical significance, the tests should be repeated at a reasonable time point and followed up until they have returned to the normal range and/or an adequate explanation of the abnormality is found.

Those repeated assessments performed outside scheduled visits will appear in listings only.

The following results will be tabulated for hematology and biochemistry tests on the safety population:

- Descriptive statistics for each test result at Baseline (V1 /Day -42), Visit 7 (M3), Visit 8 (M6) and Visit 10 (M12).
- Descriptive statistics for changes from Baseline (V1/D-42) for each test result at Visit 7 (M3), Visit 8 (M6) and Visit 10 (M12).
- Common Toxicity Criteria for Adverse Events (CTCAE version 4.03) grade at each time point and shift from Baseline (D-42) for each test result at Visit 7 (M3), Visit 8 (M6) and Visit 10 (M12). CTCAE grades for hematology and biochemistry measures will be derived according to [Appendix 3: Common Terminology Criteria for Adverse Events \(CTCAE\) grades](#).
- Shift of test abnormalities (Low, Within normal range, High) between Baseline (V1/Day-42) and Visit 7 (M3), Visit 8 (M6) and Visit 10 (M12).

The above descriptions will be repeated on each age range (4 to 5 years, 6 to 8 years, and 9 to 11 years), and each of the screening ED subgroup.

All laboratory data will be listed.

Values that are out of normal range will be flagged in the data listings.

Flags used are:

- Low (below normal ranges), based on the following original flags from the laboratory reports:
  - PL, L2 ("Panic Low")
  - TL, L1 ("Telephone Low")
  - L ("Low")
- High (above normal ranges), based on the following original flags from the laboratory reports:
  - H ("High")
  - TH, H1 ("Telephone High")
  - PH, H2 ("Panic High")

When summarized in tables, all "High" flags will be merged together ("Panic High", "Telephone High", "High"); the same for the low flags as well.

In listings, "High" and "low" flags will be reported.

Pregnancy test data will be reported only as listings.

Listings of all laboratory data will be provided by treatment group, and will include subject identifier, age, sex, weight and visit. Laboratory reference ranges will also be listed.

#### 4.9.7 Vital Signs

The following vital signs will be recorded, before each DBPCFC challenges and at V1 (D-42), V4 (D1), V5 (D8), V6 (M1), V7 (M3), V8 (M6), V10 (M12), End of study, Early termination visit and at any unscheduled visit:

- Systolic blood pressure (in mmHg),
- Diastolic blood pressure (in mmHg),

- Heart rate (beats/minute),
- Respiratory rate (breaths per minute).

The following results will be tabulated for all vital signs:

- Summary statistics of values by visit and changes from Baseline (V4 or V3 –if missing at V4-)
- Number and percentage of subjects with vital signs abnormalities at D-42, Baseline (D1), D8, M1, 3, 6 and 12 for heart rate, systolic blood pressure and diastolic blood pressure classified using the criteria defined below.

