#### **7.2.6 Visit 5 (Day 8±3 days), Visit 6 (Month 1±3 days) and Visit 9 (Month 9±7 days), Treatment Period**

The following assessments will be performed at these visits:

- Physical examination (including a complete skin examination; see [Section 6.2.4](#));
- Vital signs (see [Section 6.2.3](#));
- Spirometry (FEV1), only for Visit 9 (see [Section 6.2.5](#));
- PEF (see [Section 6.2.6](#));
- AEs recording (including volunteered or solicited AEs and AESI);
- Concomitant medications (see [Section 5.8](#));
- Check for any accidental peanut consumption (see [Section 6.4.4](#));
- Check that the subject diary has been completed accurately and ensure that the subject/parents/guardians is/are comfortable with using the diary;
- Dispense subject diary (re-instruct subject/parents/guardians on the use, if necessary; see [Section 6.2.7](#));
- Collect the treatment box dispensed at the previous visit, check the unused medication and assess medication compliance;
- Dispense a new box of study drug (re-instruct subject/parents/guardians on the proper application, timing and storage, if necessary);
- Patch adhesion Investigator's assessment : with the patch still applied, the Investigator assesses the adherence of the patch to the skin as well as the occlusion of the patch chamber;

- Check skin reactions under or around the current patch (do not remove patch) and all other zones of application and grade severity of the skin reactions (see [Table 6, Section 6.2.8](#));
- Take a photograph of the sites of application of the Viaskin® patch, load it onto the PEPITES website (described in [section 6.2.8](#)) and keep it in the subject's medical records or source documents;
- Review the use of the auto-injector of epinephrine and the anaphylaxis emergency action plan;
- Schedule next phone contact and Visit 6, Visit 7, and Visit 10 respectively.

There is no requirement for subject observation before discharge at Visits 5, 6 and 9.

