### **7.2.11 Visit 12 (2 weeks after Visit 11), End of Study Period**

The following assessments will be performed at this visit:

- Physical examination (including a complete skin examination; see [Section 6.2.4](#));
- Vital signs (see [Section 6.2.3](#));
- AEs recording (including volunteered or solicited AEs and AESI);
- Check for any accidental peanut consumption (see [Section 6.4.4](#));
- Concomitant medications (see [Section 5.8](#));
- Check subject diary.

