### **8.6.3 Vital Signs**

Observed vital sign values and changes from baseline will be descriptively summarized by visit and treatment group. All vital signs data will be listed.

The analysis of vital signs will focus on the incidence of clinically relevant abnormalities. The number of subjects evaluated and the number and percentage of subjects with clinically relevant post-baseline abnormalities at each visit will be presented. The criteria for clinically relevant post-baseline abnormalities are shown in Table 9.

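### SAP 4.9.7 omits Visit 9 (Month 9) from the vital-sign visit list and from the abnormality table, though the protocol takes vital signs then and promises abnormalities by visit

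*SAP*

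**What the plan says.** Protocol 8.6.3 makes clinically relevant abnormalities the focus of the vital-sign analysis and commits to a display by visit: "The number of subjects evaluated and the number and percentage of subjects with clinically relevant post-baseline abnormalities at each visit will be presented".

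Protocol 7.2.6 sets one common list of assessments for three visits, under the heading "Visit 5 (Day 8±3 days), Visit 6 (Month 1±3 days) and Visit 9 (Month 9±7 days), Treatment Period". Vital signs are on that list without restriction. Spirometry, by contrast, is limited to Visit 9. Vital signs are therefore required at Month 9.

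SAP 4.9.7 has two lists of visits. The first says when vital signs are recorded and goes straight from Visit 8 to Visit 10: "V7 (M3), V8 (M6), V10 (M12), End of study, Early termination visit and at any unscheduled visit". The second sets the columns of the abnormality table: "Number and percentage of subjects with vital signs abnormalities at D-42, Baseline (D1), D8, M1, 3, 6 and 12". Neither contains Visit 9.

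**The concern.** The abnormality table is the protocol's main vital-sign display, and the only one that gives percentages by treatment group for the thresholds in SAP Table 3. Visit 9 is the only scheduled site visit between Months 6 and 12; the Month 7.5 contact is a telephone call. If the SAP is programmed as written, abnormal heart rate or blood pressure readings at Month 9 are collected but never compared between active and placebo in that table, which then has no on-treatment column for half of the treatment year (12 − 6 = 6 months).

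**Working it through.** No sample size, power or alpha figure is involved. The check sets the visit lists side by side for the scheduled post-baseline visits.

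| Visit | Protocol section requiring vital signs | SAP 4.9.7 recording list | SAP 4.9.7 abnormality table |
|---|---|---|---|
| V5 (Day 8) | 7.2.6 | yes | yes |
| V6 (Month 1) | 7.2.6 | yes | yes |
| V7 (Month 3) | 7.2.8 | yes | yes |
| V8 (Month 6) | 7.2.8 | yes | yes |
| **V9 (Month 9)** | **7.2.6** | **no** | **no** |
| V10 (Month 12) | 7.2.9 | yes | yes |
| V11 (up to 1 week after V10) | 7.2.10 | only through the reference to food challenges | not named |
| V12 (2 weeks after V11) | 7.2.11 | as end of study | not named |

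**Count.** The protocol has 8 scheduled post-baseline visits with vital signs. The table names 5, so 8 − 5 = 3 are unnamed: V9, V11 and V12. V11 is the second day of the Month 12 challenge and may be meant under Month 12. V12 is off treatment. V9 is the one clear gap: of the six on-treatment time points from Day 8 to Month 12, the table has five.

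**Slip or choice?** Four things point to a slip.
- SAP 3.1 describes vital signs as a safety assessment made at every study visit.
- The next two sections, SAP 4.9.8 (physical examination) and 4.9.9 (spirometry and peak flow), both include V9.
- SAP 4.13, which collects the departures from the protocol, does not mention this table.
- Protocol 8 requires departures from the planned analyses to be described and justified, and no justification is given.

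The vital-sign row of the schedule tables did not survive text extraction well enough to be used as evidence either way.

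**Knock-on effect.** SAP 4.2 analyses an early termination assessment as if it had occurred at the next scheduled one. For a subject who stops between Months 6 and 9, the next visit in the protocol schedule is Month 9, so those termination vital signs fall out of the table too. A programmer who takes the SAP 4.9.7 recording list as the schedule might carry them to Month 12 instead. The text does not settle which.

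**The case against.** Three points can be made against the concern.

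**The data are not lost.** A reader might infer that safety data disappear. The documents do not support that. SAP 4.9.7 has all vital signs and all clinically relevant abnormalities listed by subject, and its summary statistics are specified by visit without the restricted set of dates. Protocol 6.2.3 also sends clinically relevant abnormal findings to the adverse event record. This stands, and it limits the impact. It does not remove the gap: a listing gives no percentages by arm, the investigator's judgement of relevance is not the same test as the SAP Table 3 thresholds, and because the recording list also skips V9, the by-visit summaries could be programmed without it.

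**End of study.** A reader might also infer that leaving out "Visit 12 (2 weeks after Visit 11), End of Study Period" breaks the promise of every visit in the same way. That is not established. Protocol 8.6 opens by framing safety summaries as covering the 12 months of treatment. The last patch comes off at Visit 11, and Visit 12 is attended only by subjects who do not enter the extension study. SAP 4.2 further defines the end-of-study assessment as whichever post-treatment assessment is the last available, so such a column could mix visits or describe a selected subset. Excluding Visit 12 may well be intended. The SAP should simply say so. None of this excuses Month 9, which is on treatment.

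**The table shells are not visible.** SAP Appendix 4 places the list of outputs in a separate document, so a Month 9 column may already be programmed. That limits what can be said about the practical effect, but it does not correct the SAP text.

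**Conclusion.** The concern holds for Month 9. SAP 4.9.7 leaves a protocol-scheduled, on-treatment visit out of both its recording list and its abnormality table, against Protocol 7.2.6 and 8.6.3 and with no entry in SAP 4.13. The size is one missing visit in one safety table, plus any early termination data assigned to that visit. The importance is low: listings remain, by-visit summaries should cover the visit, and no efficacy result, type I error or power is affected.

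The conclusion rests on reading the phrase in Protocol 8.6.3 as covering at least every scheduled on-treatment visit, and on the output specifications following the SAP text. Visits 11 and 12 call for clarification; the documents do not show that either was left out in error.

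**What to change.** - In SAP 4.9.7, add V9 (M9) to the list of visits at which vital signs are recorded, and add M9 to the abnormality table.
- State whether Visit 11 readings are reported under Month 12.
- State whether Visit 12 is meant to be excluded as off-treatment and attended only by subjects who do not roll over. If so, record that in SAP 4.13.
- If the omission of Month 9 was deliberate, record and justify that in SAP 4.13 as well.

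The cost is a few words in the SAP and one more visit in an existing table. No new data are needed. The correction should be made before unblinding.

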**Table 3: Criteria to Determine Clinically Relevant Abnormalities in Vital Signs**

Vital Sign Criteria for Abnormalities	Criteria for Abnormalities (any of the following situation)
Heart rate	
 
• value <60 beats/min,
 
• value >130 beats/min,
 
• an increase from pre-dosing of >20 beats/min, or
 
• a decrease from pre-dosing of >20 beats/min
 

Systolic blood pressure	
 
• value <70 mmHg
 
• value >130 mmHg,
 
• an increase from pre-dosing of > 40 mmHg, or
 
• a decrease from pre-dosing of >30 mmHg
 

Diastolic blood pressure	
 
• value <45 mmHg
 
• value >85 mmHg,
 
• an increase from pre-dosing of >30 mmHg, or
 
• a decrease from pre-dosing of >20 mmHg
 

Vital signs data and clinically relevant abnormalities in vital signs will also be listed.

#### 4.9.8 Physical Examination

A Physical examination will be performed, before each DBPCFC challenges and at V1 (D-42), V4 (D1), V5 (D8), V6 (M1), V7 (M3), V8 (M6), V9 (M9), V10 (M12), End of study, Early termination visit and at any unscheduled visit at the discretion of the investigator.

Physical examination will include the measure of the weight (kg) and height (cm) and the examination of the following:

- General appearance,
- Head and Neck,
- Ears, nose and throat,
- Eyes,
- Complete skin examination,
- Cardiovascular system,
- Respiratory system,

- Abdominal system,
- Nervous system,
- Other system(s).

The following results will be tabulated:

- Summary statistic for weight, height BMI and BSA by visit and change from Baseline (D1),
- Number and percentage of subjects with abnormal (vs. normal / not done) physical examination by visit for each of the system examined.

Physical examination data will also be listed.

#### 4.9.9 Spirometry and Peak Expiratory Flow Results

For subjects aged 6 years or older (at the date of the visit), spirometry (FEV1) will be performed at V1 (D-42), V7 (M3), V8 (M6), V9 (M9), V10 (M12), Early Termination Visit and at any unscheduled visit at the discretion of the investigator.

PEF will be performed before each DBPCFC challenge and at V1 (D-42), V4 (Baseline D1), V5 (D8), V6 (M1), V7 (M3), V8 (M6), V9 (M9), V10 (M12), Early termination visit and at any unscheduled visit at the discretion of the investigator.

The following results will be tabulated:

- Summary statistics for FEV1 value (L) and FEV1 percent predicted by visit, and change of value from Baseline (D-42) by visit,
- Summary statistics for PEF value (L) and PEF percent predicted by visit, and change of value from Baseline (D1) by visit.

All FEV1 and PEF data will be listed.

#### 4.9.10 Symptomatic Reactions during the double-blind placebo controlled food challenge (DBPCFC)

The objective symptoms collected during the DBPCFC are the following:

- Skin:
  - r Erythematous rash (and % of rash area concerned)
  - r Pruritus
  - r Urticaria/ angioedema
  - r Rash
- Upper respiratory:
  - r Sneezing/ itching
  - r Nasal congestion
  - r Rhinorrhea
  - r Laryngeal

- Lower respiratory:
  - ┆ Wheezing
- Gastrointestinal:
  - ┆ Diarrhea
  - ┆ Vomiting
- Cardiovascular
- Eyes:
  - ┆ Conjunctivitis
- Any other objective symptoms (not reported, mild, moderate, severe)

The subjective symptoms collected are:

- Itchy mouth
- Itchy throat
- Nausea
- Abdominal pain
- Any other subjective symptoms (not reported, mild, moderate, severe).

With the exception of erythematous rash (recorded as Yes/No), each symptom is graded as: 0="absent", 1="mild", 2="moderate" or 3="severe". For erythematous rash, the % area involved is collected. The grading corresponding to the area involved is captured in the grading of the "Rash" symptom. No further step is required.

A total symptom score for each subject will be calculated as the sum of all severity score for all objective symptoms (for the Peanut formula only, excluding erythematous rash and subjective complaints). This will be based on the sum of each of the following symptom being graded for severity as 0, 1, 2 or 3 (respectively absent, mild, moderate and severe):

Pruritus, Urticaria/ angioedema, Rash, Sneezing/ itching, Nasal congestion, Rhinorrhea, Laryngeal, Wheezing, Diarrhea, Vomiting, Cardiovascular, Conjunctivitis, Any other objective symptoms (one score for each of the other objective symptoms, 0 if no other objective symptom is recorded or if the answer to the question "Did the subject experienced any objective symptoms" is "No").

The reactions appearing during a DBPCFC (as they are expressly provoked) will be differentiated from those AEs occurring outside of the DBPCFC. They will be summarized group showing:

- The number and percentage of subjects with objective symptoms (by severity) at Baseline and at M12 (actual value) (overall and by type of symptom)
- The number and percentage of subjects with subjective symptoms (by severity) at Baseline and at M12 (overall and by type of symptom)
- Summary statistics on the Severity score at Baseline, at M12 (actual value) and the change from Baseline to M12 (using observed values) (excluding erythematous rash and subjective complaints).

All SAEs elicited during the entry/screening DBPCFC and Month 12 DBPCFC will be tabulated by SOC and PT and will also be listed.

#### 4.9.11 Data and Safety Monitoring Board

A Data and Safety Monitoring Board (DSMB) composed of experts in food allergy and in the methodology of clinical studies will review study safety data at specific intervals during the study and on an *ad hoc* basis. A specific DSMB meeting will be held when the first 15 subjects 4 to 5 years of age have been randomized and treated for at least 4 weeks (that is, have completed the Month 1 visit). This is to assess very early in the study that the safety of Viaskin® Peanut is acceptable in the youngest subjects. A specific SAP for DSMB meeting was prepared in addition to the present document.

